7.2 Discussion of study design

7.2.1 Study population

This study is designed to evaluate the efficacy and safety of anakinra in the treatment of gouty arthritis flares in patients for whom NSAIDs and colchicine are either contraindicated or not appropriate due to anticipated changes in patient status, not tolerated or do not provide an adequate response. Both in- and out-patients can be included in the study.

The appropriateness for treatment with NSAIDs and colchicine will depend on several factors, for example:

- Presence, severity and number of controlled and/or uncontrolled co-morbidities
- Number and type of concomitant medications
- Age of the patient
- Previous experience of therapy i.e., individual efficacy and safety outcomes

Due to the complexity of the numerous combinations of above-mentioned factors, the suitability for treatment will be assessed at the discretion of the investigator. To increase consistency, the investigators' assessment will be supported by checklists (see Appendices 4-6).

To ensure a reliable diagnosis of gouty arthritis, patients to be included in the study must meet the ACR/EULAR 2015 gout classification criteria (15).

At least one self-reported flare of gouty arthritis during the previous 12 months is required for inclusion in the study to ensure that the patients have an active gouty arthritis.

To ensure that a significant number of subsequent flares are treated in the study, the extension period will continue for all patients until 52 weeks after randomization of the last randomized patient in the study or a maximum of 104 weeks after randomization of the individual patient in the study.

The first flare of gouty arthritis to be treated in the study will be characterized by a baseline pain intensity in the index joint of ≥ 50 mm on a 0 to 100 mm VAS. This VAS cut-off ensures restriction of the study population to patients with moderate to severe pain.

For subsequent flares to be treated with IMP, a cut-off level of ≥ 30 mm on a 0 to 100 mm VAS will be used. This cut-off is based on a proposed definition for a flare based on self-reported items in patients previously diagnosed as having gouty arthritis (32). Patient-reported flare, joint pain at rest (>3 (0-10 scale)), warm joints, and swollen joints were the most strongly associated with presence of a gouty arthritis flare. The rationale behind including and, thus, giving IMP treatment to patients with lower VAS scores at subsequent flares compared to the initial flare (≥ 50 mm on a 0 to 100 mm VAS), is that the aim of the extension phase is primarily to study safety and immunogenicity, not efficacy. If gouty arthritis flares of mild pain intensity (30-50 mm on the VAS scale) were to be treated outside the study i.e. with a mix of acute gout therapies, the safety assessment of the IMP treatments would be confounded.

The required time from flare onset to treatment initiation (≤ 4 days) was selected to minimize the likelihood that a treatment effect coincide with the natural resolution of the flare (usually within 7 to 10 days).

7.2.2 Efficacy evaluation

7.2.2.1 Definition of primary endpoint

The primary endpoint is the change in patient-assessed pain intensity from baseline to 24-72 hours (average of the assessments performed at 24, 48 and 72 hours). Patients will score their pain intensity in the joint most affected at baseline (i.e. the index joint) on a 0 to 100 mm VAS.

The maximum severity of pain during a gouty arthritis flare is usually reached within 12 to 24 hours and complete resolution usually occurs within 7 to 10 days in patients with moderate to severe gouty arthritis (17). Therefore, an average of the assessments performed at 24, 48 and 72 hours over a critical period of 24 to 72 hours is proposed. The likelihood of spontaneous recovery is also lower during the early phase of a flare.

The proposed primary endpoint is in line with the FDA Guidance for Industry, Analgesic Indications: Developing Drug and Biological Products (24):

- “Efficacy endpoints in an analgesic trial should reflect direct rating of pain intensity by the patient... We recommend the use of a well-defined and reliable patient-reported outcome measure of the patient’s pain intensity” (IV.A.3 page 10)
- “...visual or numerical rating of pain intensity, or a categorical rating with several categories. It may be a single rating at a given point in time, or an average or other summary or several ratings over a period of time.” (IV.B.11.a page 25)

Patient-reported outcome is also endorsed by the Outcome Measures in Rheumatology (OMERACT) gout special interest group (8), and has been used as primary endpoint when the effect on the pain of a gouty arthritis flare has been studied with conventional, US-approved therapy such as etoricoxib and colchicine, as well as with investigational therapy such as canakinumab and rilonacept.

The comparison of primary interest is between anakinra (100 mg and 200 mg combined) and 40 mg triamcinolone. As a secondary objective, the 2 different doses of anakinra will be compared to 40 mg triamcinolone in respect to the primary endpoint, i.e. change in pain intensity from baseline to 24-72 hours.

7.2.2.2 Definitions of secondary efficacy endpoints

Response ($\geq 50\%$ change from baseline on VAS)

According to the FDA Guidance mentioned above, a responder analysis, in which the outcome for each patient is summarized as a success or a failure based on a single cut-off point can be used (24).

In this study, response is defined as a VAS pain relief of 50% or greater from baseline. In the ACR guidelines, an adequate response is defined as $\geq 50\%$ improvement in pain score at ≥ 24

hours (12). This definition has also been used in previous acute gouty arthritis studies with colchicine and canakinumab (43, 5).

Onset of effect ($\geq 20\%$ change from baseline on VAS)

Two studies in patients admitted to emergency departments with heterogeneous causes of pain have indicated that a difference of 13 mm on a VAS represents, on average, the minimum change in acute pain that is clinically significant (3, 4). In the canakinumab gouty arthritis studies, the patients had mean VAS score of approximately 70 mm at baseline. 13 mm/70 mm is less than a 20% change from baseline (5). This would justify a cut-off of $\geq 20\%$ change from baseline on VAS as clinically meaningful. In the ACR guidelines an adequate response was defined as $\geq 20\%$ improvement in pain score within 24 hours (12).

Resolution of pain in patient-assessed pain intensity (VAS <10)

In this study, resolution of pain is defined as <10 mm in pain intensity on the VAS scale.

To fully assess time to onset of effect, time to response and time to resolution of pain, the patients will record their pain assessment daily up until Day 15.

7.2.3 Comparator

According to the FDA Guidance for Industry, Analgesic Indications: Developing Drug and Biological Products“ trials intended to support a finding of efficacy for an analgesic should be designed as superiority trials. The comparator can be a lower dose of the investigational drug, a placebo or an active comparator” (24).

A gouty arthritis flare is an acute and severely painful condition, and using placebo as a comparator is not considered ethical (8).

A single i.m. dose of 40 mg triamcinolone has been selected as comparator in this study since good pain reduction has been shown when compared to canakinumab (5, 20). Furthermore, one injection of a systemic glucocorticoid eliminates the need for a glucocorticoid tapering regimen.

7.2.4 Dose and treatment duration

7.2.4.1 Dosage regimen

The pharmacokinetic (PK) profile of anakinra in adult RA patients supports once-daily s.c. administration also to patients with a gouty arthritis flare. With once daily administration, steady state serum concentrations of anakinra will almost be reached already after the first dose. As reflected in the approved label for anakinra, sufficient anakinra exposure has been maintained during a once-daily dosage interval.

7.2.4.2 Dose levels

In published case series of anakinra (see Section 10.2.1), different dose levels have been used. The majority of patients have been treated with once-daily s.c. injections of 100 mg anakinra with generally positive outcome. In the case series where patients were treated with 100 mg for 3 days, patient-assessed improvement of pain varied between 50 and 100 % (19).

In the 2 anakinra dose-response studies in patients with RA (30, 75, 150 mg (44) and 0.04, 0.1, 0.4, 1, 2 mg/kg (46)), the change from baseline in patient-reported pain intensity (a component of the primary efficacy endpoint) tended to increase with increasing doses, and the largest differences versus placebo were achieved at daily s.c. doses of 150 mg and 2 mg/kg, respectively.

Based on the results of the RA studies and the case series in acute gouty arthritis, 100 mg was selected as the lowest daily dose to be tested in this study.

The gouty arthritis population proposed to be indicated for treatment with anakinra is assumed to have a higher mean body weight than the RA patients. For reference, the mean (SD) body weight was 98 (18) kg in the canakinumab clinical studies in patients with acute gouty arthritis (N=368) (6), as compared to 77 (19) kg in the anakinra clinical study safety pool in RA patients (N=3330). As the anakinra clearance increases with increasing body weight, once-daily s.c. doses of both 100 and 200 mg will be evaluated in this study.

The safety profile of anakinra is well established and has been similar across indications and dose levels during long-term treatment (see section 5.1.4.2). Thus, a once-daily s.c. administration of 200 mg anakinra is not expected to result in an increased incidence of adverse events compared with 100 mg, the only exception being ISRs that, in studies of RA, were more frequent with s.c. doses above 100 mg.

The dose range chosen for this study may not allow discrimination based on statistically significant differences. The study will allow descriptive comparisons of efficacy and safety at 2 relevant dose levels.

7.2.4.3 Treatment duration

The treatment duration of 5 days is chosen to cover the most severe part of the flare and to minimize IMP exposure.

7.3 Selection of study population

7.3.1 Inclusion criteria

A patient must fulfill the following criteria in order to be included in the study:

1. Signed informed consent to participate in this study.
2. Male and female patients, aged ≥ 18 years
3. Patient meeting the ACR/EULAR 2015 gout classification criteria (Appendix 7 (15)).
4. History of ≥ 1 self-reported flares of gouty arthritis within 12 months prior to randomization.
5. Patient-reported, current ongoing flare of gouty arthritis characterized by baseline pain intensity in the index joint of ≥ 50 mm on a 0-100 mm VAS.
6. Currently tender (≥ 1 on a 0-4-point Likert scale) and swollen (≥ 1 on a 0-4-point Likert scale) index joint.

7. Onset of currently ongoing flare within 4 days prior to randomization.
8. The patient meets at least one of the following criteria for both treatment options NSAIDs and colchicine
 - a. At least one episode of being intolerant, or unresponsive to the treatment, see Appendices 4-6.
 - b. The investigator judges that the patient is either contraindicated or not appropriate for the treatment. Inappropriateness may be due to anticipated changes in patient status such as worsening of comorbidities or use of concomitant medication, see Appendices 4-6.
9. Criterion omitted
10. If on urate-lowering therapy, a stable dose and regimen for at least 2 weeks prior to randomization and expectance to remain on a stable dose and regimen for ≥ 2 weeks after administration of the first dose of study treatment.
11. Women of childbearing potential willing to use adequate contraception.
12. If applicable, willingness and capability to make s.c. injections at home.
13. Willingness and capability to use an electronic device for e.g. recording of pain.

Inclusion criteria for IMP treatment of *subsequent* flare(s):

14. Patient-reported, current flare of gouty arthritis characterized by pain intensity in the index joint of ≥ 30 mm on a 0–100 mm VAS, see section 7.2.1.
15. Tender (≥ 1 on a 0-4-point Likert scale) and swollen (≥ 1 on a 0-4-point Likert scale) index joint.
16. Women of childbearing potential willing to use adequate contraception.

7.3.2 Exclusion criteria

The presence of any of the following will exclude a patient from inclusion in the study:

1. Use of specified pain relief medications or biologics (including glucocorticoids, narcotics, paracetamol/acetaminophen, NSAIDs, colchicine, IL-blockers and tumor necrosis factor [TNF] inhibitors) within specified periods (see Appendix 1) prior to randomization.
2. Contraindication to triamcinolone.
3. Polyarticular gouty arthritis involving more than 4 joints.
4. Rheumatoid arthritis, evidence/suspicion of infectious/septic arthritis, or other acute inflammatory arthritis.
5. History of malignancy within the past 5 years. Exceptions are basal cell skin cancer, carcinoma-in-situ of the cervix or low-risk prostate cancer after curative therapy.
6. Known hypersensitivity to *Escherichia coli*-derived proteins, Kineret® (anakinra), Kenalog® (triamcinolone acetonide) or any components of the products.

7. Participation in another concurrent investigational study within 30 days of randomization or intake of an investigational drug within five times the half-life of that investigational drug has passed.
8. Previous inclusion in this study.
9. Known presence or suspicion of active or recurrent bacterial, fungal or viral infections, including tuberculosis, or HIV infection or hepatitis B or C infection.
10. Presence of severe renal function impairment chronic kidney disease (CKD) stages 4 and 5 (estimated creatinine clearance <30 mL/min/1.73m²).
11. Presence of neutropenia (ANC $< 1.5 \times 10^9$ /L).
12. Uncontrolled clinically significant hematologic, pulmonary, endocrine, metabolic, gastrointestinal, CNS or hepatic disease as judged by the investigator.
13. History of myocardial infarction, unstable angina, cerebrovascular events, or coronary artery bypass grafting, New York Heart Association (NYHA) class III or IV heart failure within the previous 3 months prior to Visit 1.
14. ECG with clinically relevant finding making the patient not appropriate for IMP treatment, as judged by the investigator.
15. Patients with a documented history of alcohol or substance abuse within 12 months prior to randomization (consumption of > 21 units of alcohol/week is considered alcohol abuse).
16. Patients who have undergone major surgery within 2 weeks prior to randomization, or have an unhealed operation wound/s.
17. Presence of any medical or psychological condition or laboratory result that in the opinion of the investigator might create risk to the patients (or interfere with the patient's ability to comply with the protocol requirements, or to complete the study).
18. Earlier or current treatment with anakinra.
19. Pregnant or lactating women.
20. History of >12 flares overall in the 6 months prior to randomization.

Exclusion criteria for IMP re-treatment of *subsequent* flare(s):

21. IMP treatment of latest flare initiated within the last 14 days.
22. Known presence or suspicion of active or recurrent bacterial, fungal or viral infections, including tuberculosis, or HIV infection or hepatitis B or C infection.
23. Presence of severe renal function impairment CKD stages 4 and 5 (estimated creatinine clearance <30 mL/min/1.73m²).
24. Presence of neutropenia (ANC $< 1.5 \times 10^9$ /L).
25. History of myocardial infarction, unstable angina, cerebrovascular events, or coronary artery bypass grafting, NYHA class III or IV heart failure within the previous 3 months prior to Visit 1.
26. ECG with clinically relevant finding making the patient not appropriate for IMP treatment, as judged by the investigator.
27. Patients who have undergone major surgery within 2 weeks prior to Visit 1, or have an unhealed operation wound/s.
28. Pregnant or lactating women.

29. Presence of any condition or laboratory result that in the opinion of the investigator makes the patient not appropriate for treatment with IMP.

7.3.3 Withdrawal of patients from treatment or study

7.3.3.1 Withdrawal from study treatment

A patient should be withdrawn from the study treatment if, in the opinion of the investigator, it is medically necessary, or if it is the wish of the patient.

When a patient is withdrawn from treatment, the date of the last IMP administration and the date and reason for treatment withdrawal should be clearly described in the relevant sections of the electronic case report form (eCRF). If a patient is removed from treatment because of an adverse event (AE), the reason for treatment withdrawal should always be stated as ‘adverse event’ irrespective of whether this was the investigator’s or the patient’s decision.

If a patient has been withdrawn from study treatment of one flare but fulfils the eligibility criteria for a subsequent flare, study treatment can be re-initiated. However, this is not applicable if the withdrawal from study treatment was due to a safety concern related to the IMP treatment, as judged by the investigator, see below (7.3.3.2).

All patients will continue to participate in the study and should be followed and assessed according to the protocol until the End of study follow-up call even if study treatment is discontinued unless consent is withdrawn or the patient is lost to follow-up.

7.3.3.2 Withdrawal from study

A patient can withdraw from the study at any time but should be encouraged to complete all study assessment up to Visit E, Day 28, following the last treated flare. If this is not possible an attempt should be made to examine the patient and collect relevant samples and make all relevant assessments according to the next scheduled visit.

The eCRF should be completed as far as possible .If a patient has been withdrawn from study treatment due to safety concerns as judged by the investigator to be related to IMP treatment the patient should be withdrawn from the study after Visit E.

If a patient’s treatment allocation is unblinded at the request of the investigator, IMP treatment should be stopped and the patient should be withdrawn from the study after Visit E.

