The treatment period for each flare will consist of 4 to 6 visits to the study center. The visits are the screening/baseline visit (Visit 1/Day 1), the 72-hour visit (Visit 2/Day 4), the one-week visit (Visit 3/Day 8), the two-week visit (Visit 4/Day 15), the four-week visit (Visit E/Day 28) and the 3-month visit (Visit 5/Week 12). If a subsequent flare has been treated with IMP before Day 28 and/or Week 12 visit, the Day 28 and/or Week 12 visit will be cancelled.

A follow-up by phone will be performed at 24 and 48 hours post first IMP administration to remind the patients to complete the assessments and recordings in the eDiary. A follow-up by phone will also be performed every 12 weeks following Visit 5 of the latest flare.

The patient's participation in the study will be completed by an End-of-study follow-up by phone at the end of the extension period or at the Week 12 visit of the last flare treated with IMP in the study, whichever occurs latest.

All patients will be followed throughout the study, irrespective of treatment withdrawal or use of rescue medication.

At each baseline visit (first and subsequent flares), the joint that is most affected i.e., most painful will be defined as the index joint.

Rescue medication: Patients who have difficulty in tolerating their pain are allowed to take rescue medication after the 24-hour post-dose pain assessment but not within 6 hours before the 48- and 72-hour post-dose pain assessments. Permitted rescue medication includes topical ice/cold packs, paracetamol and/or codeine or short-acting tramadol.

Patients still having insufficient relief with the rescue medication listed above after the 72-hour post-dose pain assessment are allowed to take oral prednisone or prednisolone at a starting dose up to 0.5 mg/kg per day for a maximum of 5 days.

Number of patients planned:

A maximum of 169 patients can be randomized in this study. Initially 159 patients will be randomized, 53 to triamcinolone and 106 to anakinra (53 to 100 mg and 53 to 200 mg). For each randomized patient that have not contributed with any value for analysis of the primary endpoint (e.g. no value collected for patient-assessed pain intensity from baseline to 72 hours), one extra patient can be randomized in the study. A maximum of 10 extra patients can be randomized under this protocol.

Diagnosis and main criteria for inclusion:

Main inclusion criteria:

1. Signed informed consent to participate in this study.

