1. 52 weeks after randomization of the last patient in the study

or

2. 104 weeks after randomization of the individual patient

whichever occurs first.

If the IMP treatment started week 40 or later in case 1), or week 92 weeks in case 2), the Week 12 visit will replace the End-of-study follow-up by phone.

All patients will have their follow-up visits/phone calls, irrespective of treatment withdrawal or use of rescue medication.

Subsequent flares occurring before the Day 15 visit of the latest flare (Visit 4) will be treated with permitted rescue medication i.e., no IMP will be administered.

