7.5.1.8 Day 28, Visit E

Visit E will only be performed at Day 28±2 days if no subsequent flare has occurred.

Adverse events and concomitant medication will be recorded. Blood will be collected for, immunogenicity assessments and IL-1Ra/anakinra serum concentration assessments.

7.5.1.9 Week 12, Visit 5

Visit 5 will only be performed at Week 12±5 days if no subsequent flare has occurred.

SAEs and outcomes of previously recorded AEs will be recorded and blood will be collected for CRP and SAA, immunogenicity assessments, exploratory inflammatory biomarkers and IL-1Ra/anakinra serum concentration assessments.

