### **16.2 Adverse events**

All analyses of AEs will be based on the safety population. No hypothesis testing will be performed. AEs will be coded using MedDRA Version 19.1. Percentages will be based on the number of patients in the safety population for the specific treatment group.

Since a subsequent flare can occur before the AE reporting period for the current flare has ended, the actual length of the AE reporting period can differ between patients. The actual length of the AE and the SAE reporting period will be presented by descriptive statistics for each flare and for the whole study.

A TEAE is defined as an AE with a start date/time after the first administration of IMP and not after the last day of the AE reporting period for each flare. AEs with unknown start date/time will be assumed to be treatment emergent unless the end date/time is known to be before the first administration of IMP. Pre-treatment AEs will be identified as AEs with a start date/time before the first administration of IMP (see Section 18.24).

The number and percentage of patients with at least one TEAE, at least one severe TEAE, at least one serious TEAE, including death, at least one non-serious TEAE, any related TEAE, any fatal TEAE, any TEAE leading to drug withdrawn and any TEAE leading to study withdrawal will be summarized.

The number and percentage of patients with at least one TEAE will be summarized in frequency tables by SOC and PT. This table will be repeated by BMI ( $<30.0$ ,  $\geq 30.0$  kg/m^2), sex, age ( $<65$ ,  $\geq 65$  years), race, and by ethnic origin for each flare and overall.

The number and percentage of patients with at least one TEAE will be summarized in frequency tables separately by day of onset: Day 1 to 5, Day 6 to 15 and after Day 15 by SOC and PT for each flare and overall.

The number and percentage of patients with at least one TEAE will be summarized in frequency tables by PT in descending order of frequency in the combined anakinra group for each flare and overall.

The number and percentage of patients with at least one TEAE will be summarized in frequency tables by PT, classified by maximum severity, in descending order of frequency in the combined anakinra group for each flare and overall.

The number and percentage of patients with at least one TEAE will be summarized in frequency tables by PT, classified by relationship in descending order of frequency in the combined anakinra group for each flare and overall.

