### **16.2.1 Serious adverse events**

The number and percentage of patients with serious TEAE will be presented by SOC and PT in descending order of frequency in the anakinra group for each flare and overall. The narratives will be presented in listings.

The number and percentage of patients with at least one pre-treatment SAE will be summarized in frequency tables by SOC and PT.

The number and percentage of patients with at least one SAE will be summarized in frequency tables separately by day of onset: Day 1 to Day 28 and after Day 28 for each flare and overall.

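### Protocol 7.3.3.2 removes safety-stopped and unblinded patients after Day 28, against the follow-all rule, and loses their Week 12 SAE and ADA visit

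*Protocol*

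**What the plan says.** Protocol 7.3.3.2 takes two groups out of the study after Visit E (Day 28).

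- Safety stops: where treatment ended because of "safety concerns as judged by the investigator to be related to IMP treatment the patient should be withdrawn from the study after Visit E".
- Unblinding at the investigator's request: "IMP treatment should be stopped and the patient should be withdrawn from the study after Visit E".

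Other sections give the opposite rule.

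- Protocol 7.3.3.1: patients "should be followed and assessed according to the protocol until the End of study follow-up call even if study treatment is discontinued". It names two exceptions, withdrawn consent and loss to follow-up.
- Protocol synopsis: "All patients will be followed throughout the study, irrespective of treatment withdrawal or use of rescue medication".
- Protocol 7.1, repeated in SAP 4.1: "All patients will have their follow-up visits/phone calls, irrespective of treatment withdrawal or use of rescue medication".
- Protocol 9.3.10 and SAP 9.1 likewise expect patients to stay in the study when treatment is withdrawn.

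At Visit 5 (Protocol 7.5.1.9, Week 12), "SAEs and outcomes of previously recorded AEs will be recorded and blood will be collected for CRP and SAA, immunogenicity assessments, exploratory inflammatory biomarkers". A sample for drug concentration is taken at the same visit. Protocol 7.5.6.1.2 sets Week 12 as the end of routine SAE collection.

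**The concern.** There are two problems. First, the instructions conflict, so sites may handle the same kind of patient differently. Second, if 7.3.3.2 prevails, safety follow-up is shortened because of a suspected safety problem or an emergency code break. Protocol 7.2.1 says the extension serves mainly safety and immunogenicity. Protocol 5.1.4.2 and 5.3 say that repeated short courses are little studied and might raise the risk of ADA and allergic reactions. Missing follow-up in these patients is therefore likely to be informative.

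The loss reaches planned tables. SAP 16.2.1 tabulates SAEs "separately by day of onset: Day 1 to Day 28 and after Day 28 for each flare and overall", and under SAP 16.2 "Percentages will be based on the number of patients in the safety population for the specific treatment group". A patient removed at Day 28 stays in the denominator of the later period, although SAEs not suspected to be drug-related are no longer being sought. The ADA categories in SAP 18.26 depend on the last sample, which moves from Week 12 to Day 28.

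**Working it through.** The plan gives no figure on this point, so the check compares the text and then counts visits.

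**1. Can the two rules be reconciled?** Protocol 7.3.3.1 does point to 7.3.3.2, but from the passage on restarting treatment for a later flare: a patient stopped for a drug-related safety concern may not be re-treated. The follow-up sentence comes afterwards and carries its own list of two exceptions. Removal under 7.3.3.2 is not among them. The synopsis, 7.1 and SAP 4.1 state no exception at all.

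**2. Would Visit 5 be lost for another reason?** Under Protocol 7.1, Visit 5 is cancelled when a subsequent flare has been treated. Safety-stopped patients cannot be re-treated (7.3.3.1) and unblinded patients have IMP stopped (7.3.3.2). For both groups, 7.3.3.2 is what removes the visit.

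**3. SAE collection lost per patient.** Visit E is Day 28 ± 2 days and Visit 5 is Week 12 (Day 84) ± 5 days.

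- Nominal: 84 − 28 = 56 days; 56 / 84 = 67% of the post-dose window.
- Shortest gap: (84 − 5) − (28 + 2) = 49 days.
- Longest gap: (84 + 5) − (28 − 2) = 63 days.

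**4. Samples lost per patient and flare** (Protocol 7.5.5.6, 7.5.6.5, 7.5.7.1, 7.5.8.2).

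| Sample | Scheduled | Lost |
|---|---|---|
| ADA | baseline, Days 8, 15, 28, Week 12 | 1 of 5 (1 of 4 post-dose) |
| IL-1Ra/anakinra | baseline, 72 h, Days 8, 15, 28, Week 12 | 1 of 6 |
| CRP and SAA | baseline, 72 h, Days 8, 15, Week 12 | 1 of 5 |
| Exploratory biomarkers | baseline, 72 h, Day 15, Week 12 | 1 of 4 |

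**5. Effect on ADA classes (SAP 18.26), taking a patient negative at baseline.**

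- Negative to Day 28, positive at Week 12: ADA positive with full follow-up, ADA negative if removed.
- Positive at Days 15 and 28, negative at Week 12: transient with full follow-up, persistent if removed.
- Positive at Days 8 and 15, negative at Day 28, positive at Week 12: persistent with full follow-up, transient if removed.
- First positive at Day 28, then removed: neither class, because the last sample is not negative and there are not two sequential positives. SAP 16.6.2 presents adverse events by this split.

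Misclassification can go in either direction.

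**6. How many patients?** The documents give no rate. For scale only, 1% of the 106 anakinra patients is 0.01 × 106 = 1.06, about one patient.

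**The case against.** The strongest reply is that a specific rule overrides a general one: 7.3.3.2 deals with two narrow groups, while the other statements describe the design broadly. A site might read it that way. But 7.3.3.1 is itself an operative rule with its own exceptions, and its pointer to 7.3.3.2 concerns re-treatment. Even if an exception was intended, four places fail to state it, and the loss of follow-up would remain.

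A second reply is that Day 28 is a reasonable stopping point. All-AE collection ends then for everyone. Dosing ends by Day 5 and the half-life is 4–6 hours, so Day 28 is about 23 days × 24 / 6 = 92 half-lives after the last dose, and later unrelated SAEs say little about anakinra. Later flares in these patients would also be treated outside IMP, which muddies attribution. This carries some weight for unrelated SAEs. It carries less for ADA: SAP 18.26 allows 16 weeks after the last dose for transient ADA to clear.

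Several mitigating points stand in full.

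- SAEs suspected to be related are reportable at any time (Protocol 7.5.6.1.2), and related AEs are followed after participation ends (7.5.6.1.6). The 67% therefore applies to routine SAE collection, not to all SAE information.
- Four of five ADA samples are kept.
- Week 12 CRP, SAA and biomarkers are descriptive only, and safety has no hypothesis tests.
- SAP 16.2 reports the actual length of the reporting period, so the shortening would be visible.
- The ADA shifts need particular sequences of results, for which the documents give no rate.

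None of these restores the Week 12 ADA sample or the routine collection of SAEs not judged related.

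**Conclusion.** The concern holds. The two instructions conflict, and following 7.3.3.2 costs each affected patient Visit 5, with the SAE and sample losses counted above. The primary endpoint and the Day 15 efficacy data are collected before Day 28 and are unaffected. The consequence is confined to descriptive safety and immunogenicity results, in a number of patients that is unknown and probably small. The counts assume nominal visit days and that sites apply 7.3.3.2 as written. The change is worth making because it is cheap and because the lost follow-up falls on patients who matter for the safety question; no inferential result depends on it.

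**What to change.** Reword the two sentences in Protocol 7.3.3.2. For both groups, state that IMP is permanently discontinued and that the patient remains in follow-up through Visit 5 (Week 12 SAE query, ADA and serum samples) and then to the End of study call, except where consent is withdrawn or contact is lost. This keeps the bar on re-treatment and brings 7.3.3.2 into line with 7.3.3.1, 7.1, the synopsis and SAP 4.1.

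The cost is a wording change, one visit already in the schedule, and the 12-weekly and end-of-study calls for the patients concerned. The calls could run to week 104, up to 104 − 4 = 100 weeks beyond Visit E. They add less than Visit 5 does, since they mainly record AE outcomes, but 7.3.3.1 already requires follow-up to that point. The primary analysis does not change.

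A lesser option is to write the exception into the synopsis, 7.1, 7.3.3.1 and SAP 4.1. That would remove the contradiction but leave the Week 12 data uncollected.
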